4.1 Screening/Lead-in Period

Procedures will be performed according to the Study Plan ([Table 1](#) and [Table 2](#)). Patients will be instructed to arrive in the morning of each scheduled visit. Prior to each study visit, including the Screening Visit, patients are to have fasted overnight for at least 8 hours (no food or beverage except water) (see Section 4.1.1 for information regarding fasting relative to administration of Informed Consent). Patients should delay administering their morning dose of metformin on the morning of the study-site visit. Patients are to abstain from strenuous exercise and alcohol, tobacco, and caffeine for 24 hours before visits.

4.1.1 Screening Visit (Visit 1, Week -2)

The Informed Consent for Protocol D5553C00003 will be signed prior to performing any protocol-required procedures. The Screening period will be a maximum of 14 days (Day -14 [± 7] to Day -8), depending on the availability of laboratory data from this visit. Screening procedures should be scheduled for at least 1 day later than the day of Informed Consent signature if the patient is not in a fasting state on the consent date. The following will be performed during this visit:

- IVRS will be contacted to register the patient (IVRS should be called on the day that consent is given).
- The patient's complete medical history will be recorded.
- All prior medications (prescription medications within 3 months) and concomitant medications will be reviewed.
- A complete physical exam will be conducted (refer to Section [5.2.2](#)).
- Vital signs (sitting systolic and diastolic BP and heart rate [HR]) will be measured.
- 12-lead ECG will be performed.
- Body weight and height will be measured.
- BMI will be calculated.
- Inclusion and exclusion criteria will be verified.
- Blood samples will be collected for the following assessments:
 - Serum pregnancy test (β hCG) for all female patients, unless patient has had a hysterectomy
 - Chemistry and hematology

- Serum calcitonin
 - HbA1c
 - Fasting plasma glucose
 - Fasting serum lipid concentrations (total cholesterol, low-density lipoprotein [LDL] cholesterol, high-density lipoprotein [HDL] cholesterol, non-HDL cholesterol, and triglycerides)
 - Serum creatinine (calculated creatinine clearance; Cockcroft-Gault formula)
 - Hepatitis screening (hepatitis B surface antigen, antibody to hepatitis B core antigen (anti-HBc) IgM, and hepatitis C virus antibody)
 - TSH
- Urine will be collected for urinalysis.

Individuals will be disqualified if results of any laboratory test are abnormal and clinically significant as judged by the investigator or medical monitor. Individuals may requalify for study enrollment within 2 weeks of Screening following an abnormal test result by having that test repeated once with acceptable results as judged by the investigator and medical monitor (or designee).

When all of the Screening results are available, individuals will be notified by telephone of their eligibility status.

4.1.2 Rescreening

If a patient was classified as a screen failure, the patient may be rescreened for study inclusion as long as rescreening takes place at least 3 months after the original screening visit. All patients who rescreen will be assigned a new enrollment number. If a patient will be rescreened, they must continue to meet all inclusion/exclusion criteria. They must repeat all study procedures for Visit 1 at the rescreening visit. Only 1 rescreening is permitted. If the patient does not meet all study requirements at the rescreening visit, the patient should be considered a screen failure.

4.1.3 Lead-in Period Visit (Visit 2, Week -1)

The following will be performed during this visit:

- IVRS will be contacted to register the visit.

- AEs, potential CV event triggers (Section 6.8.1), and concomitant medications will be reviewed.
- A brief physical exam will be conducted (refer to Section 5.2.2).
- Vital signs (sitting systolic and diastolic BP and HR) will be measured.
- Blood samples will be collected for the following assessments:
 - HbA1c
 - Fasting plasma glucose
- Urine will be collected for a pregnancy test for all female patients, unless patient has had a hysterectomy.
- Hypoglycemia episodes will be assessed.
- Diet and exercise counseling will be provided.
- Study-related training on use of a glucose meter will be provided. Glucose meter and supplies will be provided.
- Patient diary and instructions for completion will be provided. Patients will monitor their fasting blood glucose levels every other day and will enter the results into the patient diary. If a patient experiences a hypoglycemic episode, details regarding the episode, including symptoms of hypoglycemia, will also be recorded in the patient diary.
- Patients will be instructed on how to complete the 6-point self-monitored blood glucose (SMBG) profile. 6-point SMBG should be performed by the patient on any 3 days in the week prior to Visit 3.
- Patients will receive single-blind placebo tablets to be taken daily for the 1-week placebo lead-in period, as well as the single-blind placebo injection for the placebo lead-in period. Patients (or a designated caregiver) will be trained in administration of the study medication. Patients will be instructed to continue taking metformin as directed during this period.

4.1.4 Randomization and Baseline Visit (Visit 3, Day 0)

Prior to this visit, patients are to have fasted overnight (at least 8 hours), and to have abstained from strenuous exercise, alcohol, tobacco, and caffeine for 24 hours. Patients should delay administering their morning dose of metformin on the morning of the study-site visit. The following will be performed during this visit:

- All inclusion/exclusion criteria will be verified. INDIVIDUALS WHO DO NOT MEET ALL ENTRY CRITERIA MAY NOT BE RANDOMIZED.
- AEs, potential CV event triggers (Section 6.8.1), and concomitant medications will be reviewed.
- IVRS will be contacted for randomization of the patient. Patients will be randomly assigned to 1 of 3 treatment groups: EQW 2 mg + dapagliflozin 10 mg, EQW 2 mg + placebo, or dapagliflozin 10 mg + placebo.
- A brief physical exam will be conducted (refer to Section 5.2.2).
- Vital signs (sitting systolic and diastolic BP and HR) will be assessed.
- Body weight will be measured.
- BMI will be calculated.
- Waist circumference will be measured.
- Urine will be collected for the following assessments (to be collected right before time 0 of the meal tolerance test):
 - Urinalysis
 - Urine glucose/creatinine ratio
 - Pregnancy test for all female patients, unless patient has had a hysterectomy.
- Meal tolerance test will be performed (refer to Section 5.1.6).
- Blood samples will be collected **prior to administration of study medication** for the following assessments:
 - Chemistry and hematology
 - HbA1c
 - Fasting plasma glucose (part of meal tolerance test)
 - Fasting serum lipid concentrations (total cholesterol LDL cholesterol, HDL cholesterol, non-HDL cholesterol, and triglycerides)
 - Fasting glucagon

- Serum creatinine (calculated creatinine clearance; Cockcroft-Gault formula)
- Fasting C-peptide (part of meal tolerance test)
- Fasting insulin (part of meal tolerance test)
- Serum antibodies to exenatide
- Plasma exenatide and dapagliflozin
- Blood sample for archiving.
- DTSQ-s questionnaire will be administered.
- Patient diary will be reviewed.
- Hypo glycemia episodes will be assessed.
- Diet and exercise counseling will be provided.
- Glucose meter and supplies will be provided.
- 6-point SMBG profiles will be reviewed.
- Study medication compliance (placebo lead-in period) will be reviewed.
- Study medication will be dispensed.
- Patients (or a designated caregiver) will be trained in administration of the study medication. Study site personnel will monitor administration of study medication. Metformin should be taken by the patient with the next meal after the study visit.
- Patients (or a designated caregiver) will be provided with instructions and supplies (as appropriate) for proper transportation and storage of the study medication (to ensure temperature control, etc.).

4.2 Treatment period

After the randomization visit (Visit 3), patients will complete study visits at 1- to 4-week intervals until the end of the randomized treatment period (Visit 12, Week 28). Starting at Week 8, patients with inadequate glycemic control based on progressively stricter glycemic criteria as outlined in [Table 3](#) will remain in the study and will receive open-label rescue therapy with basal insulin.

Table 3 **Criteria for initiation of rescue therapy during the randomized treatment period**

Period	Central laboratory FPG
From Visit 7/Week 8, inclusive, up to and including the day before Visit 8/Week 12	FPG >270 mg/dL (15 mmol/L)
From Visit 8/Week 12, inclusive, up to and including the day before Visit 10/Week 20	FPG >240 mg/dL (13.2 mmol/L)
From Visit 10/Week 20, inclusive, up to and including Visit 12/Week 28 and all unscheduled visits through the day prior to Visit 13/Week 36	FPG >200 mg/dL (11.1 mmol/L)

Note: Repeat FPG testing required for confirmation before rescue initiated.

Abbreviation: FPG fasting plasma glucose

Patients with a central laboratory FPG value meeting the lack of glycemic control criterion at a pre-specified visit will be scheduled for a follow-up visit (within 3 to 5 days) to obtain a second central laboratory FPG value and review the patient's glucose meter readings. If the repeat central laboratory FPG value still meets the criterion, the patient may receive rescue therapy. Patients should continue receiving study medication while receiving rescue therapy. Patients who meet rescue criteria in the double-blind treatment period must first complete the Rescue visit procedures before receiving open-label rescue therapy, to ensure that important trial endpoint measurements are collected.

Patients who receive rescue therapy should be instructed to perform the 6-point SMBG profile before returning to the clinic for the Rescue Visit; see Section 5.1.5 for additional details.

Rescued patients with central laboratory HbA1c values >8.0% despite a maximum tolerated dose of rescue therapy for 12 weeks will be discontinued from the study and referred for additional antihyperglycemic therapy.

4.2.1 Treatment Period Visits (Visits 4 to 11, Weeks 1, 2, 4, 8, 12, 16, 20, and 24)

Prior to these visits, patients are to have fasted overnight (at least 8 hours). Patients should delay administering their morning dose of metformin and study medication on the morning of the study-site visit.

The following will be performed during these visits:

- IVRS will be contacted to register the visit.
- AEs, potential CV event triggers (Section 6.8.1), and concomitant medications will be reviewed.
- A brief physical exam will be conducted (refer to Section 5.2.2).

- Vital signs (sitting systolic and diastolic BP and HR) will be assessed.
- Body weight will be measured.
- Blood samples will be collected **prior to administration of study medication** for the following assessments:
 - Chemistry and hematology
 - HbA1c (Visits 6, 7, 8, 9, 10, and 11 only)
 - Fasting plasma glucose will be collected at all treatment visits (need for rescue will be evaluated at Visits 7 to 11 only)
 - Serum creatinine (calculated creatinine clearance; Cockcroft-Gault formula)
 - Serum antibodies to exenatide (Visits 6, 7, 8, and 10 only)
 - Plasma exenatide and dapagliflozin (Visits 6, 7, 8, and 10 only).
- Urine will be collected for the following assessments:
 - Urinalysis
 - Urine glucose/creatinine ratio
 - Pregnancy test for all female patients, unless patient has had a hysterectomy.
- Patient diary will be reviewed.
- Visit 11 only: Patients will be instructed to perform 6-point SMBG on any 3 days in the week prior to Visit 12.
- Hypoglycemia episodes will be assessed.
- Diet and exercise counseling will be provided.
- Glucose meter and supplies will be provided.
- Study medication compliance will be reviewed.
- Study medication will be dispensed every 4 weeks during the treatment period: Visits 6 to 11. Study site personnel will monitor administration of injectable study medication (if the patient is due for an injection at the time of the visit).

- Instructions, reminders, and supplies (as appropriate) will be given to the patient (or designated caregiver) for proper transportation and storage of the study medication (to ensure temperature control, etc.).
- Rescue medication will be dispensed at Visits 7 to 11 if criteria for rescue medication are met (refer to [Table 3](#)).
- Used/unused study medication will be collected every 4 weeks (Visits 6 to 11).

4.2.2 End of Treatment Period Visit (Visit 12, Week 28) or Early Termination or Rescue during Treatment Period

Prior to this visit, patients are to have fasted overnight (at least 8 hours), and to have abstained from strenuous exercise, alcohol, tobacco, and caffeine for 24 hours. Patients should delay administering the morning dose of metformin and study medication on the morning of the visit and bring OAD medication and study medication to the study-site visit.

The following procedures will be conducted:

- IVRS will be contacted to register an End of Treatment Period Visit or Early Termination visit; the IVRS will not be contacted for a Rescue visit.
- AEs, potential CV event triggers (Section [6.8.1](#)), and concomitant medications will be reviewed.
- A complete physical exam will be conducted (refer to Section [5.2.2](#)).
- Vital signs (sitting systolic and diastolic BP and HR) will be assessed.
- 12-lead ECG will be performed **prior to administration of study medication**.
- Body weight will be measured.
- BMI will be calculated.
- Waist circumference will be measured.
- Urine will be collected for the following assessments (to be collected right before time 0 of the meal tolerance test):
 - Urinalysis
 - Urine glucose/creatinine ratio.

- Meal tolerance test will be performed (refer to Section 5.1.6). (For patients who receive rescue treatment, the MTT should be performed before the rescue treatment is initiated. Also, for patients who prematurely and permanently discontinue study medication, the MTT should be performed before study medication is discontinued. After rescue therapy is initiated or study medication is discontinued, no further MTTs are required.)
- Blood samples will be collected after **administration of dapagliflozin** for the following assessments:
 - Serum pregnancy test (β hCG) for all female patients, unless patient has had a hysterectomy
 - Chemistry and hematology
 - Serum calcitonin
 - HbA1c
 - Fasting plasma glucose (need for rescue will be evaluated; part of meal tolerance test)
 - Fasting serum lipid concentrations (total cholesterol, LDL cholesterol, HDL cholesterol, non-HDL cholesterol, and triglycerides)
 - Fasting glucagon
 - Serum creatinine (calculated creatinine clearance; Cockcroft-Gault formula)
 - Fasting C-peptide (part of meal tolerance test)
 - Fasting insulin (part of meal tolerance test)
 - Serum antibodies to exenatide
 - Plasma exenatide and dapagliflozin. Samples for plasma dapagliflozin will be drawn 1 hour after administration of study medication as part of the meal tolerance test (refer to Section 5.1.6).
 - Blood sample for archiving.
- DTSQ-s questionnaire will be administered.

- SHIELD-WQ-9 questionnaire will be administered.
- Patient diary will be reviewed.
- 6-point SMBG profiles will be reviewed.
- Hypoglycemia episodes will be assessed.
- Diet and exercise counseling will be provided.
- Glucose meter and supplies will be provided (or collected).
- Study medication compliance will be reviewed.
- Study medication will be dispensed for the Extension Period if this is an End of Treatment Visit. If this is a Rescue visit, study medication for the treatment period will be dispensed if needed. Study site personnel will monitor administration of injectable study medication (if the patient is due for an injection at the time of the visit).
- Instructions, reminders, and supplies (as appropriate) will be given to the patient (or designated caregiver) for proper transportation and storage of the study medication (to ensure temperature control, etc.).
- Rescue medication will be dispensed if criteria for rescue medication are met (refer to [Table 3](#)).
- Used/unused study medication will be collected.
- A between-visit telephone contact will take place between Visits 12 to 13 for collection of safety information.

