3.2 Exclusion criteria

Patients should not enter the study if any of the following exclusion criteria are fulfilled:

Endocrine and Metabolic Conditions

1. FPG \geq 280 mg/dL (15.6 mmol/L).
2. Serum calcitonin concentration \geq 40 pg/mL (\geq 40 ng/L) at Visit 1 (Screening).
3. Clinically significant abnormal free T4 values or patients needing initiation or adjustment of thyroid treatment according to the investigator. Abnormal thyroid stimulating hormone (TSH) value at Screening will be further evaluated by free T4. Patients with clinically significant abnormal free T4 values will be excluded.
4. Known active proliferative retinopathy.

Gastrointestinal/Hepatic Conditions

5. History of, or currently have, acute or chronic pancreatitis, or have triglyceride concentrations \geq 500 mg/dL (\geq 5.65 mmol/L) at Visit 1 (Screening).
6. History or presence of inflammatory bowel disease or other severe GI diseases, particularly those which may impact gastric emptying, such as gastroparesis or pyloric stenosis.

7. History of gastric bypass surgery or gastric banding surgery, or either procedure is planned during the time period of the study. Current use of gastric balloons is also excluded.
8. Significant hepatic disease, including, but not limited to, acute hepatitis, chronic active hepatitis, or severe hepatic insufficiency, including patients with alanine aminotransferase (ALT) and/or aspartate aminotransferase (AST) >3x upper limit of normal (ULN) and/or total bilirubin (TB) >2 mg/dL (>34.2 $\mu\text{mol/L}$) (patients with TB >2 mg/dL [$>34.2 \mu\text{mol/L}$] and documented Gilbert's syndrome will be allowed to participate).
9. Known history of hepatotoxicity with any medication.
10. Known history of severe hepatobiliary disease.
11. Positive serological test for hepatitis B or hepatitis C.

Cardiovascular Conditions

12. Clinically significant cardiovascular disease or procedure within 3 months of Visit 1, including but not limited to myocardial infarction, clinically significant arrhythmia, unstable angina, coronary artery bypass surgery, or angioplasty; or are expected to require coronary artery bypass surgery or angioplasty during the course of the study.
13. Presence or history of severe congestive heart failure (New York Heart Association Class IV [[CCNYHA 1994](#)]).
14. Severe uncontrolled hypertension defined as systolic BP ≥ 180 mmHg and/or diastolic BP ≥ 110 mmHg.

Kidney Conditions

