3.6 Methods for ensuring blinding

During the Lead-in Period, patients will be treated with single-blinded placebo (tablets and injection). Patients, the investigator, study site personnel, and Sponsor personnel involved with data review and analysis will be blinded starting at Visit 3 (randomization), and will remain blinded to study treatment throughout the 28-week randomized treatment period. Only patients and investigators will remain blinded during the 24-week extension period. To preserve the blinding, access to the treatment codes will be limited to personnel not involved in the daily conduct of the trial or data review and analysis.

No member of the study team in AstraZeneca, at study sites, or any contract research organization (CRO) handling data will have access to the randomization scheme during the conduct of the study with the exception of AstraZeneca's Investigational Product Services and Patient Safety.

The randomization schedule for blinding of randomized treatment will be maintained by AstraZeneca or representative and will not be disclosed until after the first database lock at the end of the initial 28-week treatment period. AstraZeneca and its applicable representative(s) will be unblinded in Extension Periods 1 and 2 (ie, from Week 28 onwards). Sites and patients will remain blinded during Extension Periods 1 and 2.

The results for FPG, HbA1c, urine glucose/creatinine ratio, urine glucose, and urine creatinine are blinded to the investigator for all visits except Visits 1 to 3. FPG and HbA1c values are

blinded to the investigator site until the unblinding criteria for rescue therapy are met. Once the criteria are met, fasting plasma glucose and HbA1c will be reported to the site for an individual patient (ie, if FPG >270 mg/dL from Week 8 to Week 12 [excluding Week 12], or FPG >240 mg/dL from Week 12 to Week 20 [excluding Week 20], or FPG >200 mg/dL from Week 20 to Week 28 [including Week 28]). Previous values will remain blinded and the site will only receive the values going forward from the point the criteria were met.

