6.3.8 Hypoglycemia

Patients will be asked to test their blood glucose if they develop symptoms suggestive of hypoglycemia and to record specific symptoms in the patient diary. If the investigator determines that a patient experienced symptoms consistent with hypoglycemia, the event should be documented in the patient's source documentation and the hypoglycemia eCRF page (not AE eCRF page) must be completed. If a plasma or capillary glucose value of ≤ 70 mg/dL (3.9 mmol/L) is noted within the data, and the patient is asymptomatic, the investigator should assess whether the circumstances around the value are consistent with hypoglycemia. If the assessment is that the value is consistent with hypoglycemia, the hypoglycemia eCRF page should be completed. Study site personnel must obtain accurate information for the patient's file and for the hypoglycemia page of the eCRF. If the hypoglycemic episode intensity is judged to be severe, the investigator is required to contact the Sponsor.

The criteria for evaluating the intensity of a hypoglycemic episode are the following:

- MILD: Usually transient, requires no special treatment, and does not interfere with the patient's daily activities.
- MODERATE: Usually causes a low level of inconvenience or concern to the patient and may interfere with daily activities, but is usually ameliorated by simple therapeutic measures.
- SEVERE: Requires the assistance of another person to actively administer carbohydrate, glucagon, or other resuscitative actions. These episodes may be associated with sufficient neuroglycopenia to induce seizure or coma.

All hypoglycemia events will be programmatically classified as major, minor, or other hypoglycemia:

- Major hypoglycemia is an event that results in loss of consciousness, seizure or coma (or other mental status change consistent with neuroglycopenia in the judgment of the investigator or physician), which resolves after administration of glucagon or glucose. In addition, any event that requires third party assistance to resolve because of severe impairment in consciousness or behavior (whether or not symptoms of hypoglycemia are detected by patient) and is associated with a plasma or capillary glucose concentration of < 3 mmol/L (54 mg/dL) will be classified as major hypoglycemia.

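### Table 3 prints the 240 mg/dL rescue threshold (Week 12 to the day before Week 20) as 13.2 mmol/L; it equals 13.3 mmol/L, a one-digit slip with very narrow exposure

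*Protocol*

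**What the plan says.** Table 3 (section 4.2) lists three successive FPG criteria for starting open-label basal insulin in the 28-week period, each in mg/dL with a mmol/L figure in brackets. The first row reads "FPG >270 mg/dL (15 mmol/L", the second "FPG >240 mg/dL (13.2 mmol/L", and the third pairs 200 mg/dL with 11.1 mmol/L. The second row runs from Visit 8 (Week 12) to the day before Visit 10 (Week 20).

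Two other passages govern how the row is used:

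- Section 4.2 requires a second central laboratory value and a review of the patient's meter readings before rescue: "If the repeat central laboratory FPG value still meets the criterion, the patient may receive rescue therapy". Section 4.2.1 says of the visits it covers that "need for rescue will be evaluated at Visits 7 to 11 only", so the scheduled visits under this row are Visit 8 and Visit 9 (Week 16). It sends sites to Table 3 when rescue medication is dispensed.
- Section 3.6 keeps FPG and HbA1c blinded to the site until the threshold is crossed, and then releases only values from that point on. It gives the threshold in mg/dL alone: "FPG >240 mg/dL from Week 12 to Week 20 [excluding Week 20".

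**The concern.** A criterion printed in two units should be one criterion. Here the bracketed figure is lower than the mg/dL figure it is meant to restate, so a value between the two meets the row in mmol/L and fails it in mg/dL. The trial runs in the United States and other countries, so some readers can be expected to use the mmol/L figure.

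The row decides whether a patient may start insulin. For a patient who does, section 8.5.1 excludes later HbA1c values from the primary model, and section 5.1.6 requires no further meal tolerance test. That makes it an operative threshold, not background text.

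**Working it through.** **Inputs.** The protocol has five other glucose pairs: 270/15 and 200/11.1 (Table 3), "280 mg/dL (15.6 mmol/L" (section 3.2, criterion 1), "70 mg/dL (3.9 mmol/L) is noted within the data" and "3 mmol/L (54 mg/dL) will be classified as major hypoglycemia" (both section 6.3.8). Two of them give the factor directly: 270/15 = 18 and 54/3 = 18 mg/dL per mmol/L. As a second factor I use 18.016, from the molar mass of glucose (about 180.16 g/mol), a physical constant the protocol does not state.

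**Step 1: try to reproduce 13.2.** Formula: mmol/L = (mg/dL) / factor.

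| mg/dL | Printed mmol/L | Factor 18 | Factor 18.016 |
|---|---|---|---|
| 54 | 3 | 3.00 | 3.00 |
| 70 | 3.9 | 3.89 | 3.89 |
| 200 | 11.1 | 11.11 | 11.10 |
| **240** | **13.2** | **13.33** | **13.32** |
| 270 | 15 | 15.00 | 14.99 |
| 280 | 15.6 | 15.56 | 15.54 |

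A factor of 18 returns all five other pairs as printed. For 240 mg/dL both factors give 13.3, so 13.2 is not reproduced.

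**Step 2: could a different factor explain it?**

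- Rounding: 240 becomes 13.2 only if the factor lies between 240/13.25 = 18.11 and 240/13.15 = 18.25. The pair 200/11.1 allows 200/11.15 = 17.94 to 200/11.05 = 18.10. The pair 280/15.6 allows 280/15.65 = 17.89 to 280/15.55 = 18.01. Neither range overlaps the first.
- Truncation, in mmol/L per mg/dL: 200 gives 11.1 only from 11.1/200 = 0.0555 to below 11.2/200 = 0.0560. 240 gives 13.2 only from 13.2/240 = 0.0550 to below 13.3/240 = 0.0554. There is no overlap.
- The coarse multiplier 0.055 does give 240 × 0.055 = 13.2, but it would turn 200 into 11.0 and 280 into 15.4.

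**Step 3: size of the gap.** 13.2 × 18 = 237.6 and 13.2 × 18.016 = 237.8 mg/dL. The gap to 240 is 2.4 or 2.2 mg/dL, which is 1.0% or 0.9%.

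**Step 4: who could meet the gap.** Under section 3.6 a first value between 237.6 and 240 mg/dL does not open the results to the site, so the site cannot compare it with 13.2. Two cases remain: the repeat sample after a first value above 240, and a later value in a patient already opened to the site (for example, one above 270 mg/dL at Week 8 whose repeat did not confirm).

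**Step 5: which displayed values are affected.** With one decimal, a displayed 13.2 does not exceed 13.2. A displayed 13.4 means at least 13.35 mmol/L, or 13.35 × 18 = 240.3 mg/dL, and qualifies in either unit. Only 13.3 is in doubt. It stands for 13.25 to 13.35 mmol/L, which is 238.5 to 240.3 mg/dL (factor 18) or 238.7 to 240.5 mg/dL (factor 18.016). The upper end is above 240, so some of these readings qualify anyway.

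**The case against.** The arithmetic is hard to contest. The case against is about consequence, and most of it stands.

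- The correct value, 240 mg/dL, is in the same cell and in section 3.6, which controls what the site sees. This removes first values in patients not yet opened to the site.
- The decision is permissive: a confirming repeat means rescue may be given, after review of meter readings. A repeat of 238 to 240 mg/dL a few days after a value above 240 is clinically indistinguishable from a qualifying one.
- A wrong digit could be a misreading of the printed page. Other characters in the text at hand look damaged: inclusion criterion 6 shows metformin 500 mg/day where the synopsis requires at least 1500. Nothing in this row points to that, but it cannot be excluded.

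A reader might go further and infer that every FPG between 237.6 and 240 mg/dL at Week 12 or Week 16 would lead to wrongful rescue, or that the exclusion of post-rescue HbA1c carries the slip into the primary comparison. The documents do not support either reading. The section 3.6 gate and the repeat test block the first. For the second, the affected band is at most one displayed value in two visit windows, and nothing suggests that it would act differently by arm.

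**Conclusion.** The point holds as an editorial error in an operative threshold: the mmol/L figure should be 13.3. The discrepancy is 2.2 to 2.4 mg/dL. It is confined to confirmatory repeats, or later values in patients already opened to the site, read in mmol/L between Week 12 and the day before Week 20. Few patients, if any, are affected. Sample size, type I error and the primary result are untouched.

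This rests on three assumptions: the central laboratory applies the section 3.6 gate in mg/dL as written; mmol/L results are shown to one decimal; and the printed page does read 13.2. If the gate had been set at 13.2 mmol/L instead, first values in the band would be exposed too. The protocol gives no sign of that.

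**What to change.** After checking the digit against the printed table, change 13.2 to 13.3 mmol/L in the second row of Table 3. Add a note that the mg/dL value (240) governs, in line with section 3.6.

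The note is needed because 13.3 is itself rounded: 13.3 mmol/L is 239.4 to 239.6 mg/dL, and a one-decimal rule of above 13.3 would miss true values from just over 240 up to about 240.3 to 240.5 mg/dL. The cost is one digit and one line of text, with no change to conduct or analysis.
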